19.1.5 Study Populations

Intention to Treat (ITT) Population

The primary study population is the Intention to Treat (ITT) population, which consists of all randomized subjects.

Per Protocol (PP) Population

The Per Protocol (PP) population will include all randomized subjects who complete the trial without any major deviations, have worn the sensor for both Arms (Control and HCL) and have used Automode (HCL only) for ≥ 80% of the time. In addition, those subjects who take steroids after randomization will be excluded from PP population. Primary effectiveness endpoints and key secondary endpoints will be evaluated for PP Population.

Safety Population

The Safety Population will be all enrolled subjects.

19.1.6 Analysis of Endpoints

Primary Effectiveness Endpoints:

Test will be tested against the 0.025 (one-sided) significance level and both have to be met to claim success for the associated Cohort.

Group1 – Baseline A1C > 8%: Change in A1C (ΔA1C)

The initial univariate analysis for this endpoint will be an analysis of covariance at six months. If the computed F-statistic has a one-sided P<0.025 (can be computed from the two-sided F-statistic by taking the square root and comparing to a one-sided t-statistic), the null hypothesis will be rejected in favor of the alternative, Other supporting analysis including multivariable modeling may also be done to support this finding.

Group2 – Baseline A1C ≤ 8%: Time in Hypoglycemic Range

The initial univariate analysis for this endpoint will be an analysis of covariance F-test at six months. If the computed F-statistic has a one-sided P<0.025 (can be computed from the two-sided F-statistic by taking the square root and comparing to a one-sided t-statistic), the null hypothesis will be rejected in favor of the

CEP304 Clinical	Investigatio			
CEP304DOC	Revision	Н	Page 144 of 182	Medtronic

alternative. Other supporting analysis including multivariable modeling may also be done to support this finding.

CEP304 Clinical I				
CEP304DOC	Revision	Н	Page 145 of 182	Medtronic

[figure not shown]

CEP304 Clinical Inv	estigation	n Plar	1	
CEP304DOC	Revision	Н	Page 146 of 182	Medtronic

CEP304DOC	Revision	Н	Page 147 of 182	Medtronic
	_			•

CEP304 Clinical Investigation Plan CEP304DOC Revision H Page 148 of 182 Medtronic

[figure not shown]
CEP304 Clinical Investigation Plan CEP304DOC Revision H Page 149 of 182 Medtronic

CEP304 Clinical Investigation Plan CEP304DOC Revision H Page 150 of 182 Medtronic

CEP304 Clinical Inv					
CEP304DOC	Revision	Н	Page 151 of 182	Medtronic	

[figure not shown]
CEP304 Clinical Inv				
CEP304DOC	Revision	Н	Page 152 of 182	Medtronic

[figure not shown]

CEP304 Clinical Inv					
CEP304DOC	Revision	Н	Page 153 of 182	Medtronic	

CEP304DOC	Revision	Н	Page 154 of 182	Medtronic	
1					
-					

CEP304 Clinical 1				
CEP304DOC	Revision	Н	Page 156 of 182	Medtronic

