 - a) The Sensor Augmented Pump (SAP) subjects will use the MiniMed System (SAP without Low Management Suspend on Low, Low Management Suspend before low or Auto Mode) with Real Time CGM for the 6 month study period. There will be N=140.

The Continuation Period: All subjects above will enter the continuation period for 6 months using the MiniMed system with Auto Mode on.

Figure 2. Study Design

Subjects may be re-tested as per sponsor discretion.

CEP304 Clinical Investigation Plan CEP304DOC Revision Н Page 57 of 182 Medtronic

Per Cohort (CSII, MDI, or SAP), here is the numbers of subjects expected to enroll:

- A1C at time of screening:
 - \circ N = 70 A1C > 8% for HCL Arm
 - $N = 70 \text{ A1C} \le 8\% \text{ for HCL Arm}$
 - O N = 70 A1C > 8% for Control Arm
 - N = 70 A1C \leq 8% for Control Arm
- Age at time of screening:

N=Minimum number of eligible subjects for each age group within each treatment cohort		N= Minimum number of eligible Subjects for each age group and cohort	N=Minimum number of eligible subjects for each age group for study		
Age Group	Cohort	N	N	N	
	CSII				
2-6 years	SAP	No Minimum	No minimum	N= 120	
	MDI				
	CSII		No minimum	N= 180	
7 -13 years	SAP	No Minimum			
	MDI				
	CSII		N=45	N=135	
14-21 years	SAP	N= 45			
	MDI				
	CSII				
22-64 years	SAP	N= 120	N=120	N=360	
	MDI				
	CSII				
65-80 years	SAP	No Minimum	No minimum	N=150	
	MDI				

CEP304 Clinical Investigation Plan CEP304DOC Medtronic Revision Н Page 58 of 182

Table 3. Randomization

Treatment at Baseline	Randomization Options	Continuation	
CCII	CSII	uci	
CSII	HCL	HCL	
MDI -	MDI	IICI	
	HCL	HCL	
SAP -	SAP		
	HCL	HCL	

Note: Subjects 2-6 years of age will automatically enter the HCL arm at the end of the run-in period

Table 4. Site Enrollment (approximate schedule from Protocol approval)

Month Enrollment Timelines	Actual Site Enrollment (per month)	Site Enrollment Timelines
Month 1-48	April 2017 to March 2021	37
Month 49-52	April 2021 to July 2021	45

Table 5. Subject Enrollment at 2-3 month intervals (approximate schedule from first enrollment)

Month Enrollment Timelines	Actual Month Intervals	Subject Enrollment Timelines
Month 1-43	May 2017 to December 2020	930
Month 44 -50	January 2021 to June 2021	1080

CEP304 Clinical 1				
CEP304DOC	Revision	Н	Page 59 of 182	Medtronic

Month Enrollment Timelines	Actual Month Intervals	Subject Enrollment Timelines
Month 51-56	July 2021 to December 2021	1120*

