19.1.2 Endpoints and Hypotheses

Primary Safety Endpoints

The primary safety endpoint is the event rate of severe hypoglycemia and DKA from both Groups (1 & 2) during the first 6 months of study phase and second 6 months of continuation phase. The descriptive summary statistics will be presented by number of event and event rate (100 patient years) for severe hypoglycemia and DKA **separately**.

Descriptive summary (i.e. not statistically powered) for severe hypoglycemia and DKA events rates will be performed between the HCL and control arms for each age group (< 15 years, 15-25 years, and > 25 years), as well as the overall event rates.

Co-Primary Effectiveness Endpoints

The primary effectiveness endpoints consist of one-primary endpoint for each group.

Group 1 – Baseline A1C > 8%: Change in A1C (ΔA1C)

The primary effectiveness endpoints for the baseline A1C > 8% group is change in A1C from baseline to end of six-month treatment period, defined as A1C measured at the six-month treatment visit minus A1C measured at the randomization visit. The goal is to show superiority of the HCL Arm compared to the Control Arm in reducing A1C from baseline to end of six-month treatment period.

The hypothesis is mathematically expressed as:

H0: $\mu(HCL) \ge \mu(Control)$ Ha: $\mu(HCL) < \mu(Control)$

where $\mu(HCL)$ is the mean of change in A1C (%) with the HCL Arm, $\mu(Control)$ is the mean of change in A1C (%) with the Control Arm.

Group2 – Baseline A1C ≤ 8%: Time in Hypoglycemic Range

The primary effectiveness endpoint for the baseline A1C \leq 8% group is the time with SG below 70 mg/dL (3.9mmol/L) during the six-month study period, defined as percentage of SG below 70 mg/dL (3.9mmol/L) out of total number of available SG readings. The goal is to show superiority of the HCL Arm compared to the Control Arm in reducing daily time in hypoglycemic range. The hypothesis is mathematically expressed as:

CEP304 Clinical Investigation Plan CEP304DOC Revision H Page 138 of 182 Medtronic

H0: μ (HCL) ≥ μ (Control) Ha: μ (HCL) < μ (Control)

where $\mu(HCL)$ is the subject mean of time with SG below 70 mg/dL (3.9 mmol/L) in the HCL Arm, $\mu(Control)$ is the subject mean of time with SG below 70 mg/dL (3.9 mmol/L) in Control Arm.

Key Secondary Effectiveness Endpoints

Group 1 - Baseline A1C > 8%: Time in Hypoglycemic Range

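### Does the square-root-of-F shortcut for the co-primary tests let a result against HCL count as superiority?

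*Protocol*

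**What the plan says.** Protocol 19.1.6 sets the level for the two co-primary endpoints: "Test will be tested against the 0.025 (one-sided) significance level and both have to be met to claim success for the associated Cohort". The same procedure is then written for Group 1 (baseline A1C above 8%, change in A1C) and Group 2 (baseline A1C at or below 8%, time below 70 mg/dL). An analysis of covariance is run at six months, and the condition for rejection is "If the computed F-statistic has a one-sided P<0.025". A parenthesis adds that this P can be obtained from the F-statistic, and the sentence then gives the decision: "by taking the square root and comparing to a one-sided t-statistic), the null hypothesis will be rejected in favor of the" alternative.

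Protocol 5.2.1 and 19.1.2, and SAP 7.9, state that alternative. For both endpoints it is a lower mean on HCL than on Control. For Group 1, 19.1.2 puts the aim in words: "The goal is to show superiority of the HCL Arm compared to the Control Arm in reducing A1C from baseline to" six months. The visible SAP repeats the hypotheses but not the F-to-t note.

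**The concern.** With two arms the treatment F has one numerator degree of freedom and equals t squared. Its square root is therefore the absolute value of t, which is equally large whether HCL does better or worse by a given amount. The parenthesis compares this unsigned quantity with a one-sided critical value and does not say that the difference must favour HCL.

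Read on its own, the shortcut has twice the stated error rate, and a clear result against HCL could pass as superiority. These tests decide success for each Cohort and control whether the secondary endpoints are tested, so a real defect here would be serious.

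**Working it through.** **Inputs.**
- Level: one-sided 0.025 per test, both required (Protocol 19.1.6).
- Size: "N = 70 A1C > 8% for HCL Arm" and "N = 70 A1C > 8% for Control Arm", with the same numbers at or below 8%, per Cohort (Protocol, Study Design).
- Error degrees of freedom: 70 + 70 − 3 = 137. This assumes one baseline covariate, because the visible text names none.
- Harm effects of 0.3 and 0.5 SD: assumed, because the documents give none.

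**1. Reproduce the stated level.** The critical value is t(0.975, 137) = 1.977. Its square, 3.910, is the 5% critical value of F(1, 137).
- Signed rule, reject if t < −1.977: P = 0.025 under no difference. This is the protocol's figure.
- Unsigned rule, reject if √F > 1.977: P = 2 × 0.025 = 0.050, of which 0.025 is in the wrong direction. This contradicts the protocol's figure.

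A simulated analysis of covariance under no difference (20,000 runs) gave 0.024 signed and 0.047 unsigned, with 0.023 in the wrong direction. The 0.025 against 0.050 contrast does not depend on the degrees of freedom (checked from 77 to 197).

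**2. Apply the governing condition to a wrong-direction result.** Let t be the adjusted HCL minus Control difference over its standard error. Against an alternative of HCL lower than Control, the one-sided P is P(T ≤ t). If t > 1.977, this P exceeds 0.975. It is not below 0.025, so the null stands.

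**3. Find where the two readings differ.** If t is negative, √F > 1.977 holds exactly when t < −1.977, so the decisions agree. They can differ only when the estimate favours Control.

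**4. Size of the mechanical reading under true harm.** The noncentrality is d / √(2/70), where √(2/70) = 0.169.
- d = 0.3 SD: 0.3 / 0.169 = 1.77. The unsigned rule rejects with probability 0.42, the signed rule with 0.0001.
- d = 0.5 SD: 0.5 / 0.169 = 2.96. The unsigned rule rejects with probability 0.84, the signed rule with less than 0.00001.

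These are rates for a single test. Cohort success needs both groups, which contain different patients, so the probabilities multiply. With 0.3 SD of harm in one group and 0.3 SD of benefit in the other, the unsigned rule passes both with probability 0.42 × 0.42 = 0.18.

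**5. Cohort-level error under no harm.** With no effect in either group, the chance of passing both is 0.025² = 0.000625 signed and 0.05² = 0.0025 unsigned. In the worst case one group is almost certain to pass and the other has no effect. The Cohort error then equals the single-test level: 0.025 signed, 0.05 unsigned.

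**The case for a change.** The strongest case for a change is that the shortcut is complete, visible text, written twice, for the tests on which Cohort success depends. A P taken from |t| on a one-sided scale can never exceed 0.5, so it is not a proper one-sided P. Saying that only the signed reading matches the stated level concedes that the reader must add something. SAP Section 8 allows independent double programming, and two programmers could implement the note differently. A clarifying clause would cost almost nothing.

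The algebra stands, and so does the absence of a visible sign condition. What does not follow is that a harmful result would be declared superiority. The parenthesis is an optional computing note. It serves a condition that has a direction, and the direction is fixed by the hypotheses in both documents. Converting a one-degree-of-freedom F to a t with the sign of the estimate is routine shorthand.

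Two programs could disagree only when the estimate favours Control. SAP 7.9 has every endpoint summarised by mean, SD and median, so the reversal would be in plain view. A harmful effect in one group would also not open the secondary sequence by itself, because both primaries must be met.

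**Conclusion.** No change follows. This is a small gap in a computing note, and analysts fill it correctly from the stated hypothesis, aim and level. The literal shortcut has size 0.050, but the rule it serves has size 0.025, and the tail that favours HCL is exactly the stated 0.025 under either reading. The 42% and 84% rejection rates under harm are correct for the unsigned rule. They rest on assumed effects, apply to one test and not to a Cohort, and arise only if an analyst disregards the direction of the alternative. Spelling out the sign would be tidy, but it would alter no result the trial could report.

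The 137 degrees of freedom assume one covariate, which does not affect the conclusion. The public copy also lacks the protocol pages after 19.1.6 and several SAP pages before 7.10. A sign or confidence-interval rule could be there, but the conclusion does not depend on it.

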19.1.11 Coding of Adverse Events

Adverse events will be coded based on the latest version of the Medical Dictionary for Regulatory Activities (MedDRA) thesaurus.

20. Ethics

Risk Determination

In the opinion of the sponsor, this study is considered to be a significant risk (SR) study. Results of an evaluation of the requirements per 21 CFR Part 812.3, led to the SR determination as follows:

- The devices could present a potential for serious risk to subject health, safety or welfare.
- The devices are for a use of substantial importance in treating disease, and presents potential for serious risk to subject health, safety or welfare.

Therefore, for subjects 2-13 years of age, submission of an Investigational Device Exemption (IDE) application

CEP304 Clinical 1				
CEP304DOC	Revision	Н	Page 157 of 182	Medtronic

to the United States Food and Drug Administration is required

Medtronic Inc. maintains appropriate clinical study liability insurance coverage as required under applicable laws and regulations and will comply with applicable law and custom concerning specific insurance coverage. If required, a Clinical Trial Insurance statement/certificate will be provided to the IRB/EC.

Institutional Review Board (IRB) / Ethics Committee (EC)

This protocol, any subsequent amendments to this protocol, the Informed Consent/Assent form, subject material and any form of subject recruitment information (e.g. advertisements) relating to this study will be approved by the responsible EC/IRB in accordance with 21 CFR Part 56 in the US, ISO 14155:2011, Declaration of Helsinki and local ethic requirements, as applicable. The study will not start until IRB/EC approval has been granted, the Sponsor has cleared the investigational center to begin the study, and the investigational clinical staff has been appropriately trained to conduct the study. Copies of all relevant correspondence between the investigational center and the IRB/EC will be retained at investigational center and the Sponsor files.

If the ethic committee imposes any additional requirements (e.g. safety reports, progress reports etc.), Medtronic will prepare the required documents and send them to the respective authority.

Regulatory Submission

Where submission to the regulatory authority is required per local law, no patients will be enrolled in the clinical study until the particular regulatory authority has approved the current Clinical Investigation Plan of the clinical study and other documents as required according to the local requirements.

If the regulatory authority imposes any additional requirements (e.g. safety reports, progress reports etc.), Medtronic will prepare the required documents and send them to the respective authority.

Regulatory Compliance

In Canada, Europe, Australia and New Zealand this clinical study will be conducted in compliance with the Declaration of Helsinki 2013, the international standard ISO 14155:2011 ('Clinical Investigation of medical devices for human subjects'), as well as laws and regulations of the country/ies in which the clinical study is conducted (including data protection laws). Europe is also compliant with FDA regulations 21 CRF Part 11 and 21 CRF Part 54, and EU MDR.

In Canada, SOR/98-282 will also be followed.

In the US, this clinical study will be conducted in compliance with the Declaration of Helsinki 2013, the Clinical Investigation Agreement, the Clinical Investigation Plan, FDA regulations CFR, Title 21, Part 54 (Financial Disclosure by Clinical Investigators), CFR, Title 21, Part 11 (Electronic Records; Electronic Signatures), 21 CFR

CEP304 Clinical Inv				
CEP304DOC	Revision	Н	Page 158 of 182	Medtronic

Part 812 (Investigational Device Exemptions), 21 CFR Part 56 (Institutional Review Boards), 21 CFR Part 50 (Informed consents) and all other applicable federal and local regulatory requirements.

All principles of the Declaration of Helsinki have been implemented in this clinical study by means of the informed consent process, IRB/EC approval, study training, clinical trial registration, preclinical testing, risk benefit assessment, publication policy, etc.

Ethical Considerations

The sponsor will avoid improper influence on, or inducement of the subject, monitor, and investigator(s) or other parties participating in, or contributing to, the clinical study by implementing the informed consent process, Clinical Investigation Agreements and IRB/EC approval. Pediatric patients (2-21 years) will be involved in this study and will be provided with assent as applicable.

20.1 Statement(s) of Compliance

The investigator or person designated by the investigator will document and explain any deviation from the approved protocol that occurs during the course of the clinical trial. The date and reason for each deviation will be documented. (21 CFR 812.140 Records for US/ ISO14155:2011 9.6g for Europe, Australia and New Zealand)

The investigator should not implement any deviation from, or changes of, the protocol without agreement by the sponsor and prior review and documented approval/favorable opinion from the IRB/EC of an amendment, except where necessary to eliminate an immediate hazard(s) to trial subjects, or when the change(s) involves only logistical or administrative aspects of the trial (e.g., change of monitor(s), change of telephone number(s)).

The investigator may implement a deviation from, or a change in, the protocol to eliminate an immediate hazard(s) to trial subjects without prior IRB/EC approval/favorable opinion. As soon as possible, the implemented deviation or change, the reasons for it, and, if appropriate, the proposed protocol amendment(s) should be submitted:

- To the IRB/EC for review and approval/favorable opinion
- To the sponsor for agreement and, if required
- To the regulatory authority or authorities

Except in an emergency, prior approval by the sponsor, regulatory authorities and IRB/EC is required for changes in or deviations from a plan, and if these changes or deviations may affect the scientific soundness of the plan or the rights, safety, or welfare of human subjects. (21 CFR 812.35(a)) for US / ISO14155:2011 4.5.4 b))

.

CEP304 Clinical				
CEP304DOC	Revision	Н	Page 159 of 182	Medtronic

In any emergency situation the investigator shall exercise his/her judgment to safeguard the subject's interest. The investigator shall report a deviation as soon as possible to Medtronic and the reviewing IRB/EC, according to IRB/EC reporting guidelines, as applicable. Medtronic will inform the regulatory authorities, if required.

Emergency deviations must be reported to the sponsor and IRB/EC within 5 days. In Australia, clinical trials with unapproved medical devices require reporting of serious breaches by investigator and sponsor.

The following examples are deviations that could impact subject safety, affect the integrity of study data and/or affect subject's willingness to participate in the study. These deviations are significant and require immediate sponsor notification upon investigator awareness:

- Failure to obtain informed consent, i.e., there is no documentation of informed consent
- Informed consent obtained after initiation of study procedures
- Enrollment of a subject who did not meet all inclusion/exclusion criteria
- Performing study procedure not approved by the IRB/EC
- Failure to report serious adverse event to the IRB/EC and sponsor
- Investigational study device dispensed without obtaining informed consent

Medtronic is responsible for analyzing deviations, assessing their significance, and identifying any additional corrective and/or preventive actions (e.g. amend the CIP, additional training, terminate the study, etc.). Repetitive or serious investigator compliance issues may result in the need to initiate a corrective action plan, and in some cases freeze enrolment or ultimately terminate the investigator's participation in the clinical study (see section 10.9).

The investigator will propose any appropriate modification(s) of the Clinical Investigation Plan or investigational device/product or investigational device/product use. Medtronic will review this proposal and decide whether the modification(s) will be implemented.

Medtronic will submit any significant amendment to the Clinical Investigation Plan, including a justification for this amendment, to the appropriate regulatory authorities and to the investigators to obtain approval from their IRB/EC. The investigator will only implement the amendment after approval of the IRB/EC, regulatory authority and sponsor. Administrative amendments to the Clinical Investigation Plan will be submitted to the IRB/EC for notification. Furthermore investigators shall sign any approved amendment for agreement:

21. Device Deficiencies and Troubleshooting

The Medtronic 24-Hour Technical Support (TS) or local service provider will be consulted for device troubleshooting (e.g. assistance is needed by subject to operate their device(s)). When subjects call the local TS, they are instructed to notify the TS operator that they are currently participating in a clinical study. All

CEP304 Clinical 1				
CEP304DOC	Revision	Н	Page 160 of 182	Medtronic

device deficiencies that are reported to the TS will be documented by the TS staff.

Medtronic will review all device deficiencies and determine whether the deficiency requires reporting to regulatory agencies; vigilance reporting includes all devices that are CE marked in Europe. The sponsor will ensure timely Device Deficiency reporting to meet regulatory requirements.

Note: For commercially available devices, device deficiency reporting will be documented per study and relevant regulatory requirements

Depending on the country, the investigational center will be provided with a copy of all TS calls for their subjects. The TS calls should be reviewed for investigational center staff awareness and for the possibility of an AE. If an AE is detected the investigational center staff will also complete an AE eCRF.

In the US, all device deficiencies reported directly to the investigational center staff by a subject should either be reported to the TS by the subject or investigational center staff.

In Europe Canada, Australia and New Zeland all device deficiencies reported directly to the investigational center staff by a subject and should be documented on a Device Deficiency eCRF.

A device deficiency is any communication that alleges inadequacy of a medical device with respect to its identity, quality, durability, reliability, safety, or performance. NOTE: Device deficiencies include malfunctions, use errors, and inadequate labeling. (Adapted from ISO14155:2011 3.15)

In the US, Canada, Europe, Australia and New Zealand: While 24-Hour TS may direct the return/replacement of study devices, all such transactions will be managed by investigational centers directly. Subjects are asked to call the 24-Hour TS for help with the troubleshooting of devices.

It is the responsibility of the Investigator to follow the center's IRB/EC and local regulatory authority reporting requirements.

For Europe Canada, Australia and New Zealand:

Device deficiencies that did not lead to an Adverse Event, but could have led to an SADE require immediate reporting to the sponsor via completion of the applicable CRF. In addition, follow the IRB/EC and regulatory authority reporting requirements per ISO14155:2011 if any of the following apply:

- a) if either suitable action had not been taken,
- b) if intervention had not been made, or
- c) if circumstances had been less fortunate

In Australia: All device deficiencies for investigational devices with potential SADE need to be reported by investigator without unjustified delay (NHMRC Safety monitoring and reporting in clinical trials involving therapeutic goods November 2016 section C.2.b).

CEP304 Clinical				
CEP304DOC	Revision	Н	Page 161 of 182	Medtronic

22. Study Administration

